11.3.1.3 Time to first 12 or 24-week CDA

Time to 12 or 24-week CDA from core baseline to EOS (extension EOS for subjects entering the extension study or core EOS for subjects not entering the extension) is defined as:

Confidential

EudraCT 2016-004719-10 EDMS-ERI-207656619

- Increase of at least 1.5 in EDSS for subjects with a baseline EDSS score of 0;
- Increase of at least 1.0 in EDSS for subjects with a baseline EDSS score of 1.0 to 5.0;
- Increase of at least 0.5 in EDSS for subjects with a baseline EDSS score \geq 5.5;

confirmed after 12 or 24 weeks.

15 March 2022, page 137/216

Time to first 12 or 24-week CDA is defined as start date of the first 12 or 24-week CDA minus date of randomization in the core study + 1 in days. For a subject without a 12 or 24-week CDA, the censored time to 12 or 24-week CDA is defined as:

• [date of last EDSS assessment for subjects without an EDSS increase (as defined above) at their last visit or date of EDSS visit prior to the last visit if there is an increase at the last visit] minus date of randomization in the core study + 1.

Further details of the derivation of this variable will be provided in the SAP.

11.3.1.4 Cumulative number of combined unique active lesions

Cumulative number of combined unique active lesions (CUAL) [defined in Section 6.1.2] will be calculated for the following periods:

- Combined Analysis Period;
- Extension Analysis Period.

Cumulative number of CUAL is calculated as the sum of lesions at all post baseline MRI visits up to the end of each analysis period.

11.3.1.5 Longitudinal percent change over time in brain volume from baseline

Percent change in brain volume (PCBV) will be calculated at each visit using the skull as scaling constraint by performing halfway registration between images from the MRI assessments from baseline to the end of both the Combined Analysis Period and the Extension Analysis Period:

Percent change from the mean brain surface displacement between the MRI scans (SIENA method).

Further details of the derivation of this variable will be provided in the SAP.

11.3.2 Other efficacy variables

All other efficacy variables will be described in the SAP.

11.3.3 Safety variables

All safety variables will be defined in detail in the SAP. See Section 6.2 for the safety endpoint definitions.

Confidential

11.4 Description of statistical analyses

11.4.1 Overall testing strategy

15 March 2022, page 138/216

This extension study is exploratory in nature and no hypotheses are pre-specified. No multiplicity adjustments will be made for the efficacy endpoints.

11.4.2 Analysis of the main efficacy variable

11.4.2.1 Statistical model

A generalized linear model with negative binomial distribution for the number of confirmed relapses will be assumed.

- T_j denotes the length of observation for subject j
- Y_i denotes the number of relapses for subject j during t_i
- μ_i denotes the mean of the negative binomial distribution of Y_i .

The mean for the distribution of the ARR for subject j, denoted by μ_j/t_j , will be modeled by the following equation:

$$\log(\mu_j/t_j) = \mathbf{x}_j' \mathbf{\theta}_{,i.e.} \log(\mu_j) = \mathbf{x}_j' \mathbf{\theta} + \log(t_j)_{,\text{where}}$$

- \mathbf{x}_{j} is the vector denoting study treatments and covariates for subject j
- θ is the vector of unknown fixed model parameters.

A negative binomial regression model will be used to calculate the ARRs by the core study treatment for the appropriate analysis set and period. Two-sided 95% Wald CIs will be calculated for the ARRs.

11.4.2.2 Handling of missing data

All confirmed relapses from randomization in the core study up to the EOS visit in either core or extension studies for all subjects in the full analysis set (FAS) will be used in the main analysis of the ARR endpoint regardless of study treatment compliance; therefore, no data will be excluded from the analysis.

Every effort will be made to collect relapse information as completely as possible, with a focus on collecting all start dates and all EDSS/FS data required for the relapses to make a correct evaluation of relapse confirmation. All relapses with missing or incomplete start dates will be included in the efficacy analysis, unless it is clear that they have occurred prior to the start of the analysis period.

No missing data imputation is defined for the analysis of ARR variable.

11.4.2.3 Main analysis of ARR

The main statistical analysis will be performed on the FAS using all data in the Combined Analysis Period. The model described in Section 11.4.2.1 for confirmed relapses will be used, with core

15 March 2022, page 139/216

Confidential

EudraCT 2016-004719-10 EDMS-ERI-207656619

study treatment as a factor and the logarithm of time on study up to the end of the Combined Analysis Period as an offset variable. Sensitivity analysis will be described in the SAP.

11.4.2.4 Additional analyses of ARR

The same analysis as described in Section 11.4.2.3 will also be performed using all data in the Extension Analysis Period based on the EXTS with the logarithm of time on study during the Extension Analysis Period as an offset variable. The SAP will describe in more detail extension baseline covariates that will be considered in case of extension baseline imbalances.

No follow-up relapse data will be available in the extension study for subjects who discontinue study early in the core study or for subjects who complete the core study and choose not to enter the extension study, which could lead to biases in any treatment effect estimates. The SAP will describe imputation methods including a worst case, best case and most plausible case to address this.

11.4.2.5 Subgroup analyses

All subgroup analysis will be defined in the SAP.

11.4.3 Time to first confirmed relapse

The analysis of time from randomization in the core study to first relapse during the Combined Analysis Period will be performed on the FAS using Kaplan-Meier methods; estimates for the survival functions will be plotted using KM curves and will be tabulated by 12-week intervals.

11.4.4 Time to 12 and 24-week CDA

The analysis of time from core study baseline to first 12- and 24-week CDA will be summarized in a similar manner to the time to first relapse variable.

11.4.5 Cumulative number of combined unique active lesions

The statistical analysis of CUAL will be performed for each analysis period based on the associated analysis set using a similar model as described in Section 11.4.2.1 for the main analysis of the confirmed relapses with core study treatment as a factor and the log of the number of scans in the period used as an offset variable. The SAP will describe in more detail extension baseline covariates that will be considered in case of extension baseline imbalances.

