6.1.2 MRI-based endpoints

15 March 2022, page 86/216

Table 7 MRI-based endpoints

Endpoints	Combined Analysis Period	Extension Analysis Period
 PCBV at all assessments 	Y	Y
• CUAL, defined as new Gd+ T1 lesions plus new or enlarging T2 lesions without double-counting the lesions) at all assessments	Y	Y
• Number of Gd+ T1 lesions at all assessments	Y	Y
• Cumulative number of new or enlarging T2 lesions (relative to baseline) at all assessments	Y	Y
• Volume of MRI lesions (T2 lesions, T1 hypointense lesions) at all assessments	Y	Y
• Absence of MRI lesions (Gd+ T1 lesions, new or enlarging T2 lesions) at all assessments	Y	Y
 Proportion of Gd+ lesions at baseline evolving to PBHs at all assessments 	Y	Y

CUAL = cumulative number of combined unique active lesions; MRI = magnetic resonance imaging PBH = persistent black holes; PCBV = percent change from baseline in brain volume.

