11.1.1 Analysis strategy for efficacy

In order to describe the disease activity in subjects after long-term treatment with ponesimod 20 mg, and to investigate the effect of switching from teriflunomide 14 mg to ponesimod 20 mg, the main analysis of efficacy will focus on combined data from both the core and extension studies. Subjects will be analyzed according to the treatment they were randomized to in the core study. This will allow the assessment of the effect of early long-term treatment with ponesimod 20 mg compared with delaying the treatment with ponesimod 20 mg for 2 years.

Following 108 weeks of treatment with either ponesimod 20 mg or teriflunomide 14 mg in the core study, it must be assumed that the two populations will not be similar in terms of baseline characteristics at the start of the extension study, split by core study randomized treatment and overall. With this limitation acknowledged, specific efficacy endpoints will be analysed only for the extension study. Section 6.1 details which efficacy endpoints will be analysed for the combined core and extension studies, and which additionally will be analyzed for the extension study.

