11.6 Sample size

As the extension study is an extension of the confirmatory Phase 3 core study, there are no sample size statistical considerations. The sample size will be pragmatically determined by how many of the 1100 subjects planned in the core phase enroll into the extension study. Based on anticipated discontinuation rates in the core study, approximately 800 subjects are expected to enter the extension study.

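### Combined Period CUAL and ARR models name only core treatment: adding core-baseline EDSS and Gd+ lesions would gain precision, mainly for CUAL, and any extension covariates should be fixed in advance

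*Protocol*

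**What the plan says.** Protocol section 11.4.2.1 sets out a general negative binomial model whose predictor vector may hold treatments and covariates. It adds "Two-sided 95% Wald CIs will be calculated for the ARRs", by core treatment.

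The specific analyses are narrower:

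- Section 11.4.2.3, main ARR analysis (FAS, Combined Analysis Period): the model uses core "study treatment as a factor and the logarithm of time on study up to the end of the Combined Analysis Period", the latter as offset. Sensitivity analyses go to the SAP.
- Section 11.4.5, CUAL, each analysis period: "core study treatment as a factor and the log of the number of scans in the period used as an offset variable".
- Section 11.4.2.4 (extension ARR), and the same sentence in 11.4.5: the SAP will detail "extension baseline covariates that will be considered in case of extension baseline imbalances".

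Section 11.1.1 states of the two core arms that "it must be assumed that the two populations will not be similar in terms of baseline characteristics at the start of the extension study".

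The baseline values exist. Section 11.3.1.3 defines disability accumulation by baseline EDSS band, and Table 7 in section 6.1.2 lists "Proportion of Gd+ lesions at baseline evolving to PBHs at all assessments". Section 11.1.3 takes the core efficacy baseline as the last value before randomisation.

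**The concern.** Section 11.1.1 says the combined data are meant to show early against delayed ponesimod by randomised core arm. That is a comparison of two rates, and its worth lies in its precision. Section 1.4 itself describes T1 Gd+ lesions as a prognostic marker of relapses. Leaving prognostic pre-randomisation values out of the model puts their variation into the dispersion term and widens the intervals.

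The Extension Period raises a different matter. The groups there are core completers who chose to continue and met the entry criteria, so the comparison by core arm is no longer protected by randomisation. Section 11.1.1 takes dissimilarity as given, while 11.4.2.4 and 11.4.5 make adjustment wait for observed imbalance, with no threshold. If the covariates are settled only after the data are seen, the estimate depends on that choice.

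**Working it through.** **Inputs.** Section 1.3.2.3 gives the core results: ARR 0.202 vs 0.290, rate ratio 0.695 (99% limits 0.536 to 0.902), p = 0.0003; CUAL 1.405 vs 3.164 per year, rate ratio 0.44 (95% limits 0.36 to 0.54). Section 11.6 gives 1100 planned core subjects and about 800 expected extension entrants. Core treatment lasts 108 weeks (2.07 years) and the extension up to 240 weeks (4.6 years).

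**Assumptions not in the Protocol.** 550 per core arm; 400 per arm entering the extension; mean core follow-up 1.7 to 2.07 years; share of between-subject variance explained by the covariates 10, 20 or 40%.

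**Step 1: reproduce the stated p-value.** SE = ln(0.902/0.536)/(2 x 2.576) = 0.1010. z = ln(0.695)/0.1010 = -3.60, so two-sided p = 0.00032. This agrees with 0.0003, so the limits can be used.

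**Step 2: split the variance.** Var(log RR) = 1/(n r1 T) + 1/(n r2 T) + 2k/n. The first two terms are Poisson noise; the last is between-subject, with dispersion k. At n = 550 and T = 2.07:

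- CUAL: SE = ln(0.54/0.36)/(2 x 1.96) = 0.1034, variance 0.01070. Poisson part = 1/(550 x 1.405 x 2.07) + 1/(550 x 3.164 x 2.07) = 0.00090. Between-subject part 0.00980, or 92% (k = 2.69).
- ARR: variance 0.1010 squared = 0.01021. Poisson part = 1/(550 x 0.202 x 2.07) + 1/(550 x 0.290 x 2.07) = 0.00738. Between-subject part 0.00283, or 28% (k = 0.78).

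At T = 1.7 the between-subject share is 90% for CUAL and 12% for ARR (k = 0.34).

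**Step 3: effect of explaining a share s.** Relative CI width = sqrt[(Poisson + (1 - s) x between)/total]. For CUAL at s = 0.20: sqrt[(0.00090 + 0.00784)/0.01070] = 0.904.

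**Step 4: Combined Period ARR.** Per arm, 400 subjects are followed for 2.07 years plus 2.0 to 4.6 years and 150 for 1.5 years. Information per arm is the sum over subjects of mu/(1 + k mu), with k from 0.5 to 0.78. The rate pairs tried are 0.202/0.290, 0.15/0.20 and 0.202/0.202. The between-subject share is 24 to 53%. It passes half only with k = 0.78, the full 4.6 years and core rates persisting.

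Change in CI width for the log rate ratio:

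| Share explained | CUAL (core data, 2.07 y) | ARR (core data, 2.07 y) | ARR (Combined Period) |
|---|---|---|---|
| 10% | -4.7% | -1.4% | about -1 to -3% |
| 20% | -9.6% | -2.8% | about -2 to -5% |
| 40% | -20.4% | -5.7% | about -5 to -11% |

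A dispersion as low as 0.34 would make the Combined Period ARR gain smaller still.

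**The case against.** An unadjusted model for a comparison by randomised arm is not an error. Omitting baseline covariates does not in itself bias the FAS rate ratio. Nor does the Protocol forbid them: section 11.4.2.1 leaves room for covariates, and sensitivity analyses and covariate detail are sent to the SAP. All of this stands, so the absence of a covariate list is no finding. What remains is the model the Protocol does state, which names treatment and nothing else.

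Three stronger readings are tempting, and the Protocol does not support them.

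- *Between-subject variation drives most of the uncertainty for both endpoints.* True for CUAL. For ARR, relapse-count noise makes up 72 to 88% of the variance in the core period and usually more than half in the Combined Period.
- *Power is lost.* Section 11.4.1 says "This extension study is exploratory in nature and no hypotheses are pre-specified" and section 11.6 says "there are no sample size statistical considerations". Only interval width is at issue, and the stated intervals are for the ARRs themselves; none is specified for the rate ratio.
- *Everyone contributes 348 weeks (6.7 years), so the ARR gain is larger.* Section 11.1.4.2 ends follow-up of non-entrants at core EOS, section 11.6 expects about 800 of 1100 to enter, and sections 3.2.3 and 3.2.3.1 stop treatment early where ponesimod is marketed.

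On the extension, it is fair to say that section 11.1.1 presents dissimilarity as an acknowledged limitation and that the SAP may fix the list and trigger. It also stands that extension-baseline values come after randomisation and may be affected by core treatment. Adjusting for them changes what is estimated and does not restore randomised comparability, so adjusted results should not simply replace unadjusted ones.

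**Conclusion.** The point holds as one of precision and pre-specification, not of bias. For CUAL the gain is material: about 5, 10 or 20% narrower intervals if the covariates explain 10, 20 or 40% of the between-subject variance. For Combined Period ARR it is small, about 1-3, 2-5 or 5-11%. The imbalance trigger for the Extension Period sits badly with section 11.1.1 and should be settled in advance.

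The sizes rest on planned rather than actual numbers, equal allocation, assumed follow-up, and an assumed share explained, for which the Protocol gives no figure. The Protocol also does not say whether the core limits came from a covariate-adjusted model. If they did, the dispersion derived here is already residual: the unadjusted between-subject share would be higher, and the percentages could not be read as the gain from the same covariates.

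**What to change.** **Combined Period (11.4.2.3 and 11.4.5).** Add core-baseline EDSS and core-baseline Gd+ T1 lesions (presence or number, chosen in advance) to the CUAL and ARR models. Report standardised rates by core arm and the rate ratio with 95% CI. Keep the treatment-only model as supportive.

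**Extension Period (11.4.2.4 and 11.4.5).** Replace the imbalance trigger with a covariate set fixed in advance. Report adjusted and unadjusted results side by side, and state that the covariates are post-randomisation, with the consequence for interpretation. Table 1 schedules EDSS but no MRI at Visit 1, so an extension-baseline Gd+ value would be the last core scan, as section 11.1.3 allows.

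**Cost.** Some wording, a few model terms and a second set of estimates. The one small downside is that subjects without a baseline MRI need a stated rule, for example a missing category. No new data collection is needed.

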11.4.6 Percent change from baseline in brain volume

PCBV will be summarized descriptively by core treatment group for the Combined Analysis Period using the FAS and for the Extension Analysis Period for the EXTS.

11.4.7 Analysis of the other efficacy variables

The analysis of all other efficacy variables will be detailed in the SAP.

15 March 2022, page 140/216

EudraCT 2016-004719-10 EDMS-ERI-207656619

Confidential

11.4.8 Analysis of the safety variables

If not otherwise stated, only safety data considered treatment-emergent (up to 15 days after the last treatment administration) in the respective analysis period [as defined in Section 11.1.4] will be included in tables and figures. All safety data will be included in listings, with flags for safety data not considered to be treatment-emergent to a specific analysis period.

Generally, safety data is presented as follows:

Safety data collected in the extension study will be analyzed based on the **Extension Analysis Period** using the EXTS and will be summarized for all subjects overall and split by core study treatment group. The analysis of change from baseline for safety endpoints assessed by visit will use the extension baseline as reference.

Furthermore, the long-term safety of ponesimod 20 mg and the changes in safety for teriflunomide 14 mg subjects switching to ponesimod 20 mg will be assessed by summarizing all data in the **Combined Analysis Period** using the SAF. Cumulative data such as AEs and SAEs will only be summarized for subjects initially treated with ponesimod 20 mg in the core study. Safety endpoints assessed by visit will be summarized by core study treatment group. Analysis of change from baseline for safety endpoints assessed by visit will use the core baseline as reference.

11.4.8.1 Adverse events

All AEs will be coded using the latest version of MedDRA available at the time of database closure.

11.4.8.1.1 Treatment-emergent AEs and SAEs

Treatment-emergent AEs and SAEs will be tabulated by system organ class (SOC) and preferred terms within each SOC: the number and percentage of subjects who experienced at least one (S)AE, at least one (S)AE within each SOC and at least one S(AE) within each preferred term will be displayed. (S)AEs will also be summarized by decreasing frequency of preferred term. (S)AEs will also be tabulated by maximum intensity and relationship to study treatment.

AEs and SAEs will be summarized over the:

- Extension Analysis Period by core study treatment and overall, using the EXTS;
- Combined Analysis Period for subjects who received ponesimod 20 mg in the core study only, using the SAF.

11.4.8.1.2 AEs of special interest and MACE

AEs of special interest and MACE will be summarized in the same way as described in Section 11.4.8.1.1. The list of AEs of special interest is provided in Appendix 4.

EudraCT 2016-004719-10 EDMS-ERI-207656619

Confidential

15 March 2022, page 141/216

11.4.8.1.3 AEs leading to premature discontinuation of study treatment

(S)AEs leading to premature discontinuation of study treatment will be summarized by core study treatment and overall for the Extension Analysis Period based only on the EXTS, in a similar manner as that described in Section 11.4.8.1.1.

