4.2 Inclusion criteria

- 1. Signed informed consent, prior to initiation of any study-mandated procedure.
- 2. Subjects with MS having completed the double-blind treatment in the core study as scheduled (i.e., who completed the double-blind treatment period until Week 108).
- 3. Compliance with the teriflunomide elimination procedure assessed as sufficient by the investigator at visit FU1 or abbreviated visit FU2 of the core study, whichever occurred last (the recommended compliance should include intake of 33 doses of cholestyramine (8 g or 4 g) or 22 doses of activated charcoal (50 g).
- 4. For subjects of reproductive potential: #
 - Women of childbearing potential (WOCBP):
 - Must have a negative pre-treatment urine pregnancy test on Day 1;
 - Must agree to undertake 4-weekly urine pregnancy tests during the study and until 6 weeks after the first of two consecutive tests showing teriflunomide plasma level <0.02 mg/L and until at least 30 days after study treatment discontinuation;
 - Must have been using reliable methods of contraception uninterrupted since EOT in the core study and must agree to continue using reliable methods of contraception

EudraCT 2016-004719-10 EDMS-ERI-207656619

Confidential

15 March 2022, page 60/216

throughout the study until 6 weeks after the first of two consecutive tests showing teriflunomide plasma level <0.02 mg/L and until at least 30 days after discontinuation of study treatment.

• Fertile male subjects participating in the study who are sexually active with WOCBP must agree to use a condom until 6 weeks after the first of two consecutive tests confirming plasma teriflunomide level <0.02 mg/L.

Definition of WOCBP, fertile male subjects and the acceptable methods of contraception for this study are described in Section 4.4.

Women who interrupt the study treatment because of planned pregnancy will be exempt from any protocol-mandated pregnancy tests after the first positive urine pregnancy test and until 30 days before study drug re-initiation. These women will also interrupt contraception 30 days after the study treatment interruption and until after delivery [see Section 5.1.12.4].

The inclusion criterion 4 was valid for all subjects throughout the recruitment period. Following approval of protocol version 5 (by which time all subjects had been off teriflunomide for over 2 years), teriflunomide plasma testing is no longer required.

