6.2 Safety endpoints

In order to investigate the long-term safety of ponesimod and the changes in safety in teriflunomide subjects switching to ponesimod 20 mg, analysis will be performed on all data in the core and extension studies combined, using the core baseline as a reference. In addition, safety data

15 March 2022, page 87/216

reference.

EudraCT 2016-004719-10 EDMS-ERI-207656619

Confidential

collected in the extension study will be analyzed independently, using the extension baseline as a

Table 9 details which endpoints will be analyzed for the Extension Analysis Period, and which for the Combined Analysis Period.

Table 9 Analysis of safety endpoints

Endpoints	Combined Analysis Period	Extension Analysis Period
Adverse events		
 Treatment-emergent AEs, SAEs, and AEs of special interest[#] AEs leading to premature discontinuation of study treatment 	Y* Y	Y Y
Cardiac safety		
• Treatment-emergent morphological ECG abnormalities (as defined by the ECG provider)	Y*	Y
 Absolute values by visit for 12-lead ECG parameters (HR, PR, QRS, QT, QTcB, QTcF) 	Y	Y
 Change from baseline values by visit for ECG parameters (HR, PR, QRS, QT, QT QTcB, QTcF) 	Y	Y
 Change in ECG parameters (HR, PR, QRS, QT, QT QTcB, QTcF) from pre-dose to selected post-dose assessments (1 h, 2 h, 3 h, 4 h) on Day 1 and on day of re-initiation of study treatment 	N	Y
Pulmonary safety		
• Absolute values and percent change from baseline in FEV ₁ and FVC at all assessments	Y	Y
• Treatment-emergent decrease from baseline $>20\%$ and $>30\%$ in FEV ₁ or FVC	Y	Y
• Treatment-emergent decrease from baseline >20 percentage points in % of predicted FEV ₁ and FVC	Y	Y
• Among subjects with a decrease of ≥ 200 mL or $\geq 12\%$ in FEV ₁ or FVC from baseline to EOT, reversibility defined as a decrease of < 200 mL or $< 12\%$ in FEV ₁ or FVC from baseline to EOS**	Y	N

15 March 2022, page 88/216

EudraCT 2016-004719-10 EDMS-ERI-207656619

Confidential

Table 9

Analysis of safety endpoints

Endpoints	Combined Analysis Period	Extension Analysis Period
 Absolute change from baseline to EOS versus change from baseline to EOT in FEV₁ and FVC (absolute and % of predicted)** 	Y	N
• Change in lung diffusion capacity as assessed by DL _{CO} (at selected sites only) expressed in absolute change (mL) and % of predicted value from baseline at all assessments	Y	Y
• Change from baseline to EOS versus change from baseline to EOT in DL _{CO} (absolute and % of predicted) (at selected sites only)**	Y	N

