11.1.2 Analysis strategy for safety

The long-term safety of ponesimod and the changes in safety in teriflunomide 14 mg subjects switching to ponesimod 20 mg will be investigated by summarizing the combined data from both the core and extension studies. Cumulative data such as AEs and SAEs will only be summarized for subjects initially treated with ponesimod 20 mg in the core study to allow a long-term assessment of up to 6 years. To assess trends over time and to assess the switch from teriflunomide 14 mg to ponesimod 20 mg, the analysis of the change from baseline for safety endpoints will be assessed by visit from core baseline up to last treatment + 15 days, and will be analyzed by core treatment group.

In addition, all safety data collected in the extension study will be analyzed for the extension study only, and will be summarized both overall and split by the core treatment group. For this analysis, the extension study baseline is used as the reference.

Section 6.2 details which safety endpoints will be analyzed for the combined core and extension studies, and which will be analyzed for the extension study.

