11.2 Analysis sets

11.2.1 Extension Set

The Extension Set (EXTS) includes all subjects who signed an informed consent to enter the extension study and who received at least one dose of ponesimod study medication in the extension study.

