11.4.8.2.3 Change from pre-dose to post-dose

The change from pre-dose to post-dose assessments at 1 h, 2 h, 3 h, and 4 h on the day of initiation of ponesimod in the extension study will be summarized by core study treatment and overall for the following parameters: HR, PR, QT, QTcB, QTcF. This analysis will be based on the Extension Analysis Period using the EXTS.

EudraCT 2016-004719-10 EDMS-ERI-207656619

Confidential

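### Table 9 assigns AE discontinuations to both analysis periods, but Section 11.4.8.1.3 analyses them only in the Extension Set, which cannot contain any core-study AE discontinuation

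*Protocol*

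**What the plan says.** The protocol synopsis names "AEs leading to premature discontinuation of study treatment" among the main safety endpoints. In Section 6.2 the same endpoint has its own row in Table 9, with a Y for the Combined Analysis Period and a Y for the Extension Analysis Period.

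Table 9 is meant to be binding on this. Section 6.2 introduces it with "Table 9 details which endpoints will be analyzed for the Extension Analysis Period, and which for the Combined Analysis Period", and Section 11.1.2 refers back to it: "Section 6.2 details which safety endpoints will be analyzed for the combined core and extension studies, and which will be analyzed for the extension study".

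Section 11.4.8.1.3 gives the analysis: these events are summarised "by core study treatment and overall for the Extension Analysis Period based only on the EXTS". No Combined Period analysis is given there. The Extension Set takes in consenting subjects "who received at least one dose of ponesimod study medication in the extension study" (Section 11.2.1). Inclusion criterion 2 in Section 4.2 admits "Subjects with MS having completed the double-blind treatment in the core study as scheduled", which it explains as reaching Week 108.

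On a related row, Table 9 lists pre-dose to post-dose ECG change for Day 1 and for days of re-initiation. Section 11.4.8.2.3 says that the change "on the day of initiation of ponesimod in the extension study will be summarized by core study treatment and overall" and mentions no other day.

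**The concern.** Both instructions cannot be followed. If Section 11.4.8.1.3 is followed, a main safety endpoint loses the long-term view that Section 11.1.2 sets out for cumulative safety data in core ponesimod subjects, an assessment of up to six years.

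The loss is selective. Stopping for an AE is a direct measure of tolerability, and the first safety objective is long-term safety and tolerability. A core ponesimod subject who stopped early for an AE is kept out of the Extension Set by the entry rule itself. The core ponesimod column of this summary therefore describes people already shown to tolerate about two years of the drug, and nothing in Section 11.4.8.1.3 tells the reader so.

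**Working it through.** **Text comparison for the neighbouring safety analyses**

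| Analysis | Combined Period | Extension Period |
|---|---|---|
| AEs and SAEs (11.4.8.1.1) | Safety Set, core ponesimod subjects | Extension Set |
| Special-interest AEs and MACE (11.4.8.1.2, by cross-reference) | as above | as above |
| AE discontinuations, Table 9 | Y | Y |
| AE discontinuations, 11.4.8.1.3 | none | Extension Set only |
| Pulmonary withdrawals (11.4.8.3.5) | core ponesimod subjects | not stated |

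The general AE-discontinuation analysis is out of line both with Table 9 and with the two sections just before it.

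**Who can be counted.** The Extension Set needs at least one extension dose. Extension entry needs double-blind treatment completed to Week 108. A subject who permanently stopped core treatment early therefore cannot be in the set. The Combined Period for safety (Section 11.1.4.2), by contrast, expressly keeps core data from subjects who did not enter the extension.

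**How many are outside.** Inputs: 1100 planned in the core and about 800 expected in the extension (Section 11.6); about half of core subjects on teriflunomide (Section 5.1.7). The 800 cannot be reproduced, because the anticipated core discontinuation rate is not given; only the implied non-entry can be worked back.

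- All subjects: 1100 − 800 = 300, and 300/1100 = 27.3%.
- Core ponesimod arm at 1:1: 1100/2 = 550 planned, 800/2 = 400 entering, so about 150 outside.

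These are non-entrants for any reason, including completers who chose not to continue.

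**Possible effect, core ponesimod arm (assumed rates, none in the protocol).** Let c be the proportion of 550 stopping for an AE in the core study and x the proportion of 400 stopping for an AE in the extension. The Extension Set counts 400x; the Combined Period counts 550c + 400x; the share missed is 550c/(550c + 400x).

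- c = 3%, x = 10%: 16.5/(16.5 + 40) = 29%.
- c = 15%, x = 3%: 82.5/(82.5 + 12) = 87%.
- Over c from 3% to 15% and x from 3% to 10%, the Combined Period proportion runs from 28.5/550 = 5% to 122.5/550 = 22%, against 3% to 10% of 400 in the Extension Set.

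The range is wide because the protocol gives no AE-discontinuation rate. The direction does not depend on the assumed rates: the core events counted are zero by design.

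**ECG row.** Core ponesimod subjects reach extension Day 1 after at least 14 days off drug (Section 3.2.3), and Section 1.4 describes re-initiation in terms of that restart. Section 11.4.8.2.3 analyses that day by core treatment, so its core ponesimod column is a re-initiation analysis. Only later, mid-study re-initiation days, also in the Table 9 row, are left out.

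**The case against.** Several counter-arguments have force.

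- **Other summaries cover the core period.** AEs, SAEs, special-interest AEs and MACE are tabulated over the Combined Period, pulmonary withdrawals likewise, and all safety data are listed (Section 11.4.8). Core events do not vanish from the report. This stands, but none of these is the general AE-discontinuation summary that Table 9 requires.
- **The first 108 weeks were reported in a completed randomised study.** True, but the core report cannot give a cumulative figure across both studies.
- **The restriction may be deliberate.** The wording in Section 11.4.8.1.3 is emphatic. If intended, the correction would be N in Table 9 with a reason, and the long-term assessment would lose this endpoint.
- **Early ponesimod discontinuations are visible in switchers.** Former teriflunomide subjects start ponesimod on extension Day 1, and results are shown by core treatment. This stands and limits the point to the core ponesimod arm.

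A reader might go further and infer that the Extension Set understates ponesimod discontinuation by a known factor. The protocol does not support that. Suppose hazards of 4% per year for the first 2.07 years (108 weeks) and 1% per year after. Over 4.60 extension years (240 weeks), the core ponesimod column gives 1 − exp(−0.01 × 4.60) = 4.5%. Switchers give 1 − exp(−0.04 × 2.07 − 0.01 × 2.53) = 10.2%, and a 50:50 set about 7.4%. With 3% then 1.5% per year the corresponding figures are 6.7%, 9.5% and about 8.1%. Setting such figures against a 6.7-year cumulative incidence also mixes different follow-up lengths.

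A reader might also infer that re-initiation gets no ECG analysis. It does, on extension Day 1.

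**Conclusion.** The contradiction between Table 9 and Section 11.4.8.1.3 is real and should be resolved before analysis. Followed as written, Section 11.4.8.1.3 makes the general AE-discontinuation summary for the core ponesimod arm conditional on completing about two years of treatment.

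On the planning figures and 1:1 allocation, about 150 of about 550 core ponesimod subjects are outside the Extension Set. That is an upper bound on the core AE discontinuers excluded in that arm under these figures, not an estimate. The figure of 300 non-entrants covers both arms and should not be read as lost ponesimod discontinuations.

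The study is descriptive with no pre-specified hypotheses, so no error rate or power is affected; what is at stake is how the tolerability figure is read. The ECG point is secondary: a wording mismatch over later re-initiation days, not a lost objective.

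**What to change.** 1. In Section 11.4.8.1.3, add a Combined Analysis Period summary of AEs leading to premature discontinuation, on the Safety Set, for subjects who received ponesimod 20 mg in the core study, in the form used in Section 11.4.8.1.1.
2. Add to the Table 9 row the asterisk already used for the AE/SAE row, so that the Combined Period column is plainly limited to core ponesimod subjects, in line with the cumulative-data rule in Sections 11.1.2 and 11.4.8.
3. Keep the Extension Set table, and state in its title or footnote that for the core ponesimod group it is conditional on core completion.
4. In Section 11.4.8.2.3, add the later re-initiation days listed in Table 9. Identify the subjects for whom post-dose monitoring was mandated, since Sections 5.1.9 and 8.5.3 require it only for those with cardiovascular risk factors.

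The cost is a few sentences and one or two more descriptive tables. No new data are needed: Section 11 already provides for combining the two databases.
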